9. ADMINISTRATIVE REQUIREMENTS

9.1 Product Complaints

A product complaint is a verbal, written, or electronic expression that implies dissatisfaction regarding the identity, strength, purity, quality, or stability of a drug product. Individuals who identify a potential product complaint situation should immediately contact MedComm Solutions (see below) and report the event. Whenever possible, the associated product should be maintained in accordance with the label instructions pending further guidance from a Millennium Quality representative.

For Product Complaints,

- Phone: [name] ([name])
- E-mail: [contact]
- [contact]
- Hours: Mon-Fri, 8 a.m. – 6 p.m. ET

Product complaints in and of themselves are not AEs. If a product complaint results in an SAE, an SAE form should be completed and sent to Millennium Pharmacovigilance

11. APPENDICES

11.1 Eastern Cooperative Oncology Group (ECOG) Scale for Performance Status

Grade	Description
0	Normal activity. Fully active, able to carry on all predisease performance without restriction
1	Symptoms but ambulatory. Restricted in physically strenuous activity, but ambulatory and able to carry out work of a light or sedentary nature (eg, light housework, office work)
2	In bed < 50% of the time. Ambulatory and capable of all self-care, but unable to carry out any work activities. Up and about more than 50% of waking hours.
3	In bed > 50% of the time. Capable of only limited self-care, confined to bed or chair more than 50% of waking hours.
4	100% bedridden. Completely disabled. Cannot carry on any self-care. Totally confined to bed or chair
5	Dead

Source: Oken MM, Creech RH, Tormey DC, Horton J, Davis TE, McFadden ET et al. Toxicity and response criteria of the Eastern Cooperative Oncology Group. *Am J Clin Oncol* 1982; 5 (6):649-55.

Karnofsky Performance Status Scale

The following table presents the Karnofsky performance status scale¹:

Points	Description
100	Normal, no complaints, no evidence of disease
90	Able to carry on normal activity
80	Normal activity with effort; some signs or symptoms of disease
70	Cares for self; unable to carry on normal activity or to do active work
60	Requires occasional assistance but is able to care for most of his/her needs
50	Requires considerable assistance and frequent medical care
40	Disabled; requires special care and assistance
30	Severely disabled; hospitalization indicated. Death not imminent
20	Very sick; hospitalization necessary; active support treatment necessary
10	Moribund; fatal processes progressing rapidly
0	Dead

¹ Mor V, Laliberte L, Morris JN, Wiemann M. The Karnofsky Performance Status Scale: an examination of its reliability and validity in a research setting. *Cancer* 1984;53:2002-2007.

11.2 Cockcroft-Gault Equation

For males:

$$\text{Creatinine Clearance} = \frac{(140 - \text{age}[\text{years}] \times \text{weight} [\text{kg}])}{72 \times (\text{serum creatinine}[\text{mg/dL}])} \quad \text{OR} \quad \frac{(140 - \text{age}[\text{years}] \times \text{weight} [\text{kg}])}{0.81 \times (\text{serum creatinine}[\mu\text{mol/L}])}$$

For females:

$$\text{Creatinine Clearance} = \frac{0.85 (140 - \text{age}[\text{years}] \times \text{weight} [\text{kg}])}{72 \times (\text{serum creatinine}[\text{mg/dL}])} \quad \text{OR} \quad \frac{0.85 (140 - \text{age}[\text{years}] \times \text{weight} [\text{kg}])}{0.81 \times (\text{serum creatinine}[\mu\text{mol/L}])}$$

Source: Cockcroft DW, Gault MH. Prediction of creatinine clearance from serum creatinine. Nephron 1976;16(1):31-41.

11.3 Pharmacokinetic (PK) Sample Collection and Handling (Mandatory, if Applicable)

Materials and Labeling

Blood samples for PK assessment must be collected in 3-mL Vacutainer tubes containing K2EDTA as the anticoagulant. Resulting blood and plasma PK samples must be stored in plastic storage tubes with caps. No blood collection tubes with separation gel should be used.

Collected tumor samples will be dissected to a size of roughly 200-300 mg. The samples are weighed, wrapped in aluminum foil, and flash frozen on a dry ice acetone bath. The frozen samples are stored at -70 C and shipped on dry ice to the CRO for bioanalysis.

. All containers and tubes must be labeled. The printed information must include the study number, patient identification number, treatment period, and scheduled sampling day and time. No other information will be written on the labels.

Preparation of Plasma Pharmacokinetic Samples

1. Draw blood into labeled and chilled 3 mL lavender top K2EDTA Vacutainer tube.
2. Mix the blood with the anticoagulant by gently inverting the tube 8-10 times and immediately place on wet ice.
3. Centrifuge the blood samples for 10 minutes at 1006g at 4° C in a refrigerated centrifuge within 10 mins of sample collection
4. Immediately following centrifugation, gently remove the plasma from the packed cells and aliquot into two transfer vial filled with lyophilized citric acid. Each aliquot should contain exactly 0.5 mL of plasma.
5. Vortex split tubes thoroughly. Any remaining plasma post split1/split 2 sample aliquots should be discarded following appropriate biohazard disposal procedures.

NOTE: If < 0.5 mL plasma is obtained post centrifugation, do not process or store split1 or split2, record split1: ISV (Insufficient Sample Volume), split2: ISV. If < 1.0 mL plasma is obtained post centrifugation, process and store split1 according to procedure; do not process or store split2, record split 2: ISV. Discard remaining plasma using appropriate biohazard waste disposal procedures.

6. Replace cap on tube and freeze the samples immediately at -70°C

Note: No more than 60 minutes should elapse between blood collection and freezing the plasma samples.

7. Keep samples frozen at -70°C or lower until shipment.

Note: Wet ice is defined as a mixture of ice and water

Radius of rotation (rotor arm length) (cm)	RPM speed needed to achieve 1000g
4	4743
5	4242
6	3873
7	3585
8	3354
9	3162
10	3000
11	2860
12	2738
13	2631
14	2535
15	2449

Excel formula if rotor length not listed in above table:

$$\text{RPM} = \text{SQRT}((1006 / (0.00001118 * \text{rotor length in cm}))^2)$$

Questions regarding handling the plasma pharmacokinetic specimens should be addressed to the contact person designated by Millennium.

Shipment of Pharmacokinetic Tissue and Blood Samples

All pharmacokinetic samples must be sent to the bioanalytical laboratories specified below in a single shipment at the end of the study or in multiple shipments as agreed upon with the lab (MLN9708 PK samples currently have 618 days of stability and will need to be analyzed before reaching the end of their stability). An inventory list must be included with each shipment. The inventory list must note each specimen drawn for each patient, and note any missing specimens.

The investigator must follow the instructions below:

- For all international shipments, a courier will be designated.
- Notify the bioanalytical laboratories and the designated courier at least 24 hours in

Emory University IRB _____
Takeda Oncology Clinical Study Protocol [X16071]

advance of the planned shipment. Provide the designated courier with the appropriate account number to be used, if applicable.

- Samples should be shipped via overnight delivery only on Monday through Wednesday, excluding holidays.
- Double-bag the frozen samples for each patient in bags that can withstand dry ice conditions.
- Pack the frozen samples in sufficient quantity of dry ice in appropriate containers, to maintain a frozen state for at least 3 days.
- Avoid direct contact between sample bags and dry ice by separating them with a dry ice resistant material (eg, newspaper).
- For all biological samples, follow the International Air Transport Association (IATA) regulations for shipment.
- Ensure that the total package weight does not exceed 27.2 kg (60 pounds).
- Label the package with the sponsor-investigator name and study number.
- Include a return address (which includes the investigator's name) on the outside of each shipping container.
- Comply with all courier regulations for the shipment of biological specimens (include all paperwork).
- Retain all documents indicating date, time, and signature(s) of person(s) making the shipment in the study files.

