**WINSHIP CANCER INSTITUTE OF EMORY UNIVERSITY
INVESTIGATOR-INITIATED STUDY
WITH
MILLENNIUM PHARMACEUTICALS
INVESTIGATIONAL AGENT: IXAZOMIB**

CLINICAL STUDY PROTOCOL
Takeda Oncology Clinical Study Protocol X16071
Phase 0 Analysis of Ixazomib (MLN9708) in Patients with Glioblastoma

Indication: Glioblastoma
Phase: Phase 0

Protocol History

Draft	26 Jan 2015
Original	DD Month YYYY

Investigator and Study Center:
[name]
Department of Neurosurgery
Emory University School of Medicine
[name]
[name]
[contact]

[figure not shown]
This is an investigator-initiated study. The principal investigator, [name] (who may also be referred to as the sponsor-investigator), is conducting the study and acting as the sponsor. Therefore, the legal/ethical obligations of the principal investigator include both those of a sponsor and those of an investigator.

PROTOCOL SUMMARY

Study Title: Phase 0 Analysis of Ixazomib (MLN9708) in Patients with Glioblastoma
Phase: 0
Number of Patients: 3
Study Objectives Primary 
1. Measurement of tissue concentration of ixazomib in a glioblastoma after preoperative administration2. Measurement of blood and plasma concentration of ixazomib during surgical sampling after preoperative administration Secondary 
1. Assessment of the safety of ixazomib after single dose administration in glioblastoma patients undergoing surgery for tissue concentration assessment.
Overview of Study Design: This is a surgically based Phase 0 study of MLN9708 administration in 3 patients to determine whether its active metabolite MLN2238 can be measured in tumor in individuals with glioblastoma. The primary endpoint centers around MLN2238 concentration measurements in the glioblastoma, blood and plasma of these individuals 3 hours after administration.

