1.4 Pharmacokinetics and Drug Metabolism

Clinical IV and PO PK data show that ixazomib citrate (measured as the biologically active boronic acid form of ixazomib [MLN2238]) has multi-exponential disposition with a rapid initial phase that is largely over by 4 hours. Oral ixazomib citrate is rapidly absorbed with a median single-dose first time of occurrence of maximum (peak) concentration (T_{max}) of approximately 0.5 to 2.0 hours and a terminal disposition half-life ($t_{1/2}$) after multiple dosing of approximately 5 to 7 days [10]. Results of a population PK analysis (n = 137) show that there is no relationship between body surface area (BSA) or body weight and clearance (CL). Also, based on stochastic simulations for fixed dose, exposures are independent of the individual patient's BSA [11]. Based on these data, a recommendation was made for fixed dosing in clinical trials. An absolute bioavailability of 67% was determined for ixazomib using the population PK analysis. Please refer to the current ixazomib IB and Safety Management Attachment (SMA) for information on the PK doses of ixazomib.

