3. STUDY ENDPOINTS

3.1 Primary Endpoints

Determination of brain tumor tissue, blood and plasma concentrations ixazomib

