4. STUDY DESIGN

4.1 Overview of Study Design

Individuals who are candidates for surgery for recurrent (or progressive) glioblastoma will be considered for participation in this study. Those deemed by the PI to be potential candidates will be counseled and provided a consent. Those signing a consent will then undergo eligibility screening. Those eligible will receive 4 mg of Ixazomib orally 3 hours prior to surgery and be on study as of that day. Tumor samples will be obtained at the time of surgery and provided to Covance for MLN2238 assay. Also during the surgery, blood samples will be obtained at the time of induction, one and two hours later and provided to Covance for ixazomib assay in both blood and plasma. At the time of return to the outpatient clinic the individual will be assessed for safetyrelated to Ixazomib administration. At that point the individual will be off study. Adverse events are followed and reported for 30 days after drug administration. The subject will continue to follow-up with their surgeon and oncologist as per standard care for their circumstance and therapy dictates and the adverse events will be captured at those follow-up visits.

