6.11 Study Treatment

Schedule of Events and Observations

	Consent	Screening	Ixazomib Administration 3 Hours Before Surgery	Surgery	Postop Day 1	Postop Visit for Staple/Suture Removal
Reference Time Line	14 or fewer days before date of surgery	After consent and prior to ixazomib administration	1 to 3 hours prior to surgical incision	On average a two to four hour period of time with sampling occurring as clinically safe during the tumor resection	Assessment 12 to 36 hours after the end of the surgery	Depending on the nature of the wound repair and integrity staple/suture removal will occur 10 to 20 days after the day of surgery
Patient Education	x					
Laboratory screening		x				
Observation for clinical and laboratory toxicity using standard postop parameters*			x		x	x
Blood sampling just prior to incision				x		
Blood sampling during tumor sampling				x		
Blood sampling during surgical closure				x		
Tumor sampling				x		
* Toxicities are to be assessed according to the NCI Common Terminology Criteria for Adverse Events (CTCAE), version 4.03.						

Informed Consent Process: Patients with recurrent glioblastoma who need surgery will be presented the concept of this study and its pro's and con's. They will then receive a consent form and be allowed to review it. They will then be allowed to ask questions and provided these are satisfactorily answered sign consent. This process may take one or more days.

Screening: After signing informed consent there will be determination of performance status, CBC, Complete Metabolic Panel, Na/K/Glucose/Chloride/Bun/Cr, PT/PTT/INR, Urinalysis, & Serum pregnancy test.

Ixazomib Administration: 4.0 mg Ixazomib administration orally with 8 oz of water 3 hours prior to projected surgery start time. The individual will be observed for evidence of treatment-emergent adverse events. This will be recorded as the on study time. Accurate recording of the time of ixazomib administration will be made in the patient's clinical records.

Surgery: One red top tube of blood will be collected at the time of surgical incision, tumor sampling and wound closure. The time of each sampling will be recorded. The tumor will be sampled at three different sites and the timing of the sampling will be recorded.

Post Op Day 1: General and neurologic exam observations will be collected and laboratory evaluations performed will be collected and recorded.

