7. STATISTICAL AND QUANTITATIVE ANALYSES

7.1 Statistical Methods

This will be a phase 0 study designed to assess whether or not Ixazomib reaches glioblastoma tissue in measurable concentrations. The drug concentration results and clinical observations after administration will be tabulated and summarized with simple descriptive statistics. The relationship between patient's demographic, tumor and drug concentration results will be assessed with Pearson's correlation coefficient and tested with Wald's test. In addition, the mean and standard error of the concentrations will be estimated using a random-effects model to account for the within-patient correlation of the tumor biopsy samples. Given the limited number of observations, a relatively simple covariance matrix (e.g. compound symmetry) will be assumed.

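### The plan asks whether ixazomib is measurable in tumor but specifies no tumor-to-blood comparison or residual-blood allowance, so a low positive reading cannot be interpreted

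*Combined protocol and SAP*

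**What the plan says.** **The question.** The Protocol Summary gives the aim as "to determine whether its active metabolite MLN2238 can be measured in tumor in individuals with glioblastoma". Section 7.1 calls the study "designed to assess whether or not Ixazomib reaches glioblastoma tissue in measurable concentrations". The primary endpoint in Section 3.1 is "Determination of brain tumor tissue, blood and plasma concentrations ixazomib". None of these places states a minimum concentration, an assay limit or a tumor-to-blood ratio.

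**The specimens.** Section 6.11: "The tumor will be sampled at three different sites and the timing of the sampling will be recorded". Appendix 11.3: "Collected tumor samples will be dissected to a size of roughly 200-300 mg", and then "The samples are weighed, wrapped in aluminum foil, and flash frozen on a dry ice acetone bath". Storage at -70 C and shipment on dry ice follow. The list has no step that rinses or blots the tissue or measures its blood content.

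**The blood samples.** Section 4.1 has them "provided to Covance for ixazomib assay in both blood and plasma".

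**The analysis.** Section 7.1 plans tabulation, descriptive statistics, correlations with patient and tumor characteristics, and a random-effects mean and standard error across the tumor samples. Section 7.1.5 analyzes each tumor site separately with descriptive statistics. Section 7.1.3 discards data after a specimen-handling problem but does not name residual blood or give a test for it.

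**The concern.** Resected tumor contains some blood. If it is frozen as it comes, the assay reads tissue and blood together. Drug is still circulating at sampling: Section 1.4 gives a median Tmax of about 0.5 to 2.0 hours and a terminal half-life of 5 to 7 days after multiple dosing, and sampling takes place a few hours after the dose. A drug that stayed in the vessels could then give a measurable tumor value.

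Replication does not help. This is a bias rather than noise, and it runs upward wherever the tissue level is below the blood level. Three sites in three patients cannot average it out, and the random-effects model would estimate the mean of a mixture of tissue and blood.

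Section 1.9 says the study should settle whether the active metabolite reaches these tumors before later-phase work begins. The interpretation of a low reading is therefore what is at stake.

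**Working it through.** The plan has no figure of its own to reproduce: three patients were chosen on clinical judgment (Section 7.1.1), and no assay limit or expected concentration is given.

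**Inputs**
- Specimen mass: 200-300 mg (Appendix 11.3).
- Blood fraction of the specimen, v: not in the documents. Assumed 2%, 5% and 10%, with density about 1.
- Blood concentration and tissue lower limit of quantification (LLOQ): not in the documents. Kept as symbols, with illustrative values where marked.

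**Step 1: mixing.** Observed C_tumor = (1-v) × true tissue level + v × C_blood. Dividing by C_blood, with r the true tissue-to-blood ratio:

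apparent ratio = (1-v)r + v

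The excess over the truth is v(1-r), which is positive whenever r is below 1.

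| True r | v = 2% | v = 5% | v = 10% |
|---|---|---|---|
| 0 | 0.020 | 0.050 | 0.100 |
| 0.05 | 0.069 (1.38-fold) | 0.098 (1.95-fold) | 0.145 (2.90-fold) |
| 0.30 | 0.314 (1.05-fold) | 0.335 (1.12-fold) | 0.370 (1.23-fold) |

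For example, at r = 0.05 and v = 10%: 0.90 × 0.05 + 0.10 = 0.145, and 0.145/0.05 = 2.90.

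**Step 2: when zero penetration reads as measurable.** With r = 0 the specimen shows v × C_blood, so it reaches the LLOQ once C_blood is at least LLOQ/v. That is 50 times the LLOQ at 2%, 20 times at 5% and 10 times at 10%.

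Illustrations with assumed values:
- LLOQ 0.5 ng/g and v = 5%: a blood level of 10 ng/mL is enough (0.05 × 10 = 0.5).
- LLOQ 1 ng/g and v = 2%: 20 ng/mL is not enough (0.02 × 20 = 0.4).

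The artefact is possible but not certain.

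**Step 3: what an allowance does.** C_corr = (C_tumor - v × C_blood)/(1-v). As ratios to blood:

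| Observed ratio | v = 2% | v = 5% | v = 10% |
|---|---|---|---|
| 0.05 | 0.031 | 0.000 | -0.056 |
| 0.10 | 0.082 | 0.053 | 0.000 |
| 0.20 | 0.184 | 0.158 | 0.111 |
| 0.50 | 0.490 | 0.474 | 0.444 |

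The allowance can decide the reading at observed ratios of about 0.10 or less. It matters little at high ratios.

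**Step 4: should the 10% value be a pass/fail rule?** Suppose the true blood fraction is 2% and the correction uses 10%. The corrected ratio is (0.98r + 0.02 - 0.10)/0.90 = (0.98r - 0.08)/0.90, which is zero or negative for every true r up to 0.08/0.98 = 0.082. With a true blood fraction of 5% it is (0.95r - 0.05)/0.90, zero or negative up to 0.053. A true ratio of 0.05 would be declared absent in both cases (-0.034 and -0.003). Such a rule replaces a possible false positive with a possible false negative.

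**Step 5: is a matched blood value assured?** The correction needs whole blood drawn when the tumor is sampled.
- Section 4.1 draws at induction and one and two hours later.
- The schedule of events and Section 6.11 draw around incision, at tumor sampling and at closure. Section 6.11 specifies a red top tube.
- Appendix 11.3 requires 3-mL K2EDTA tubes. It mentions storing blood and plasma, but its numbered steps prepare plasma only.

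As written, a matched whole-blood value is intended in one place and not assured overall.

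**The case against.** - **The comparator is already there.** Blood and plasma concentrations are primary measurements, and Section 7.1 tabulates the drug concentration results without limiting them to tumor. A reader might infer that the plan looks at tumor values alone. It does not, and anyone with the tables could divide one column by another. This stands. What is missing is a pre-specified ratio and an allowance for blood.
- **There is no go rule.** A reader might infer that any measurable value counts as success, so that a false-positive signal is built in. The documents set no threshold or decision rule, and actual concentrations will be reported. This stands too: the defect is that a low value cannot be interpreted, not that a wrong decision is programmed.
- **Circulating drug need not be high at sampling.** Section 1.4 describes a "rapid initial phase that is largely over by 4 hours", and Section 4.1 gives the dose 3 hours before surgery, with tumor taken later still. The schedule's window of 1 to 3 hours before incision could bring sampling closer to the peak, and the two statements of timing need to be reconciled. The documents support circulating drug being present. They do not show that it is high.
- **Residual blood is inferred from silence.** Appendix 11.3 lists no step to deal with it, but the bioanalytical laboratory's method is not in these documents and might address it. That is a reason to state the method in the plan.
- **The blood fraction is an assumption.** This is true, and it is why the result belongs in a sensitivity range and not in a single corrected figure or a binding rule.

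**Conclusion.** The point holds as a limit on interpretation. The plan asks a detection question, lists no control for residual blood and pre-specifies no comparison that would expose it. Under an assumed blood fraction of 2-10%, apparent tumor-to-blood ratios up to 0.10 are compatible with no penetration at all, while ratios well above that are little affected. Whether a falsely measurable value would occur in this trial cannot be determined, because the blood fraction, blood level and tissue LLOQ are not given. The improvement is worth making because it uses concentrations the plan already intends to measure, and because with three patients a ratio or correction chosen after the data are seen would carry little weight.

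**What to change.** **Section 7.1.5.** Add, for each tumor site:
1. The tumor-to-whole-blood and tumor-to-plasma ratios, using the blood drawn at tumor sampling.
2. A sensitivity analysis, C_corr = (C_tumor - v × C_blood)/(1-v), at v = 2%, 5% and 10%, stated in advance to be assumed values and reported beside the tissue assay's LLOQ.
3. A statement that a site where C_corr falls below the LLOQ anywhere in that range is described as inconclusive for penetration, not negative. The 10% value is not a pass/fail criterion.

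**Sections 4.1 and 6.11, the schedule of events and Appendix 11.3.** Reconcile the blood draw times and tube types, and state how whole blood is aliquoted and stored, so that a whole-blood value matched to tumor sampling exists.

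**Cost.** A paragraph of analysis text, a few lines of calculation, the LLOQ from the laboratory, and the reconciliation of the sampling sections. The downside is that the adjusted figures rest on an assumed range, and some low readings may be reported as inconclusive.

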2. STUDY OBJECTIVES

2.1 Primary Objectives

1. Measurement of tissue concentration of ixazomib in a glioblastoma after preoperative administration
2. Measurement of blood and plasma concentration of ixazomib during surgical sampling after preoperative administration

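### Whole blood is a primary matrix, but the only written blood procedure (Appendix 11.3) prepares plasma alone, so following it yields no whole-blood sample

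*Combined protocol and SAP*

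**What the plan says.** Whole blood is named separately from plasma at each level of the plan. Section 2.1 gives the second primary objective as "Measurement of blood and plasma concentration of ixazomib during surgical sampling after preoperative administration". Section 3.1 gives the endpoint as "Determination of brain tumor tissue, blood and plasma concentrations ixazomib". Section 4.1 says that the intraoperative samples are "provided to Covance for ixazomib assay in both blood and plasma". The Protocol Summary repeats both matrices.

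For collection, section 6.11 states: "One red top tube of blood will be collected at the time of surgical incision, tumor sampling and wound closure". Appendix 11.3 specifies a different tube: "Blood samples for PK assessment must be collected in 3-mL Vacutainer tubes containing K2EDTA as the anticoagulant".

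For storage, the appendix says: "Resulting blood and plasma PK samples must be stored in plastic storage tubes with caps". The numbered steps that follow are headed as plasma preparation. They draw a 3 mL tube, mix it, place it on wet ice and centrifuge it within 10 minutes of collection. The next step is: "Immediately following centrifugation, gently remove the plasma from the packed cells and aliquot into two transfer vial filled with lyophilized citric acid". Each plasma aliquot is 0.5 mL, and surplus plasma is discarded. The insufficient-volume rule and the 60-minute limit to freezing are both written for plasma.

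**The concern.** The plan asks for two blood matrices but writes instructions for one. With one tube per time point, the plasma procedure uses the whole tube, and once the plasma has been drawn off the cells there is no whole blood left to send. Staff who follow the numbered steps would ship plasma only.

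One of the three matrices in the primary endpoint would then have no data, and the blood part of the second primary objective would go unanswered. Each patient has one dose and one operation, so the samples cannot be retaken. Section 7.1.3 adds a consequence: where pharmacokinetic data are missing and irretrievable, a replacement subject is recruited. Read literally, that could apply to missing whole-blood values in a study planned for three patients.

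**Working it through.** There is no calculated figure in the plan to reproduce: section 7.1.1 bases the sample size of three on clinical judgment. The check has two parts.

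**1. Each blood matrix traced through the plan**

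- Objective (2.1), endpoint (3.1) and assay (4.1): blood yes, plasma yes.
- Collection (6.11): one tube per time, for both matrices.
- Preparation steps (11.3): blood none; plasma in two 0.5 mL splits.
- Stabilizer (11.3): blood none stated; plasma in citric-acid vials.
- Time limit and freezing (11.3): blood none stated; plasma frozen at -70°C within 60 minutes.
- Storage container (11.3): blood and plasma both named.
- Shipment (11.3): the heading names tissue and blood. It omits plasma, which is plainly shipped, so blood there may be a general label.

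Counts: 3 patients (4.2) x 3 times (6.11) x 1 tube = 9 tubes. Section 4.1 describes the times differently (induction, then one and two hours later) but also gives three draws. Following the steps yields up to 9 x 2 = 18 plasma vials and 0 whole-blood aliquots.

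**2. Whether one 3 mL tube could supply both matrices**

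The documents give no hematocrit (h) or plasma recovery (r). I assume h from 27% to 50% and r from 80% to 100%. Two plasma splits need 2 x 0.5 = 1.0 mL.

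Plasma from a full tube = 3.0 x (1 - h) x r:
- h = 27%, r = 100%: 3.0 x 0.73 = 2.19 mL
- h = 50%, r = 80%: 3.0 x 0.50 x 0.80 = 1.20 mL

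Whole blood that can be spared while keeping both splits = 3.0 - 1.0 / [(1 - h) x r]:
- h = 27%, r = 100%: 3.0 - 1.37 = 1.63 mL
- h = 40%, r = 100%: 3.0 - 1.67 = 1.33 mL
- h = 40%, r = 80%: 3.0 - 2.08 = 0.92 mL
- h = 50%, r = 80%: 3.0 - 2.50 = 0.50 mL

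Plasma left after an illustrative 0.5 mL whole-blood aliquot = 2.5 x (1 - h) x r:
- h = 27%, r = 100%: 1.83 mL
- h = 50%, r = 100%: 1.25 mL
- h = 50%, r = 80%: 1.00 mL, exactly the amount needed
- h = 50%, r = 75% (just outside the assumed range): 0.94 mL, at which the appendix's own rule drops the second split

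A pre-spin aliquot is therefore feasible over the assumed range, but the margin falls to zero at its unfavorable end.

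**The case against.** A reader might infer that the plan excludes whole blood, or that whole-blood concentration cannot be measured. The documents do not support that. Appendix 11.3 requires blood samples to be stored, section 4.1 plans a blood assay, and the volume check shows that an aliquot before the spin is possible. Staff who noticed the storage sentence could take one. This part of the objection stands: the defect is an incomplete instruction, and the loss is conditional on following the steps as written. It does not remove the problem. The storage sentence is a container rule only, and an improvised aliquot would have no set volume, stabilizer or time limit, so handling could differ among the three patients.

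It can also be said that the steps sit under a plasma heading and so do not claim to cover every tube, and that 6.11 and 11.3 disagree on tube type, which makes any combined workflow uncertain. Both are fair. But 6.11 provides only one tube per time, and 11.3 requires pharmacokinetic blood to be drawn into K2EDTA. The red-top tube therefore cannot be presumed to be a separate whole-blood tube. The disagreement is a further reason to amend.

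Finally, section 7.1 frames the study around whether the drug reaches tumor tissue in measurable concentrations, and 7.1.5 states the primary objective as tumor concentration. That limits the damage, because tumor and plasma results do not depend on the missing step. Whole blood nevertheless remains a named part of the primary endpoint.

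**Conclusion.** The gap is real and should be closed before the first patient is dosed. Followed as written, the steps give whole blood at 0 of 9 planned draws, none of which can be repeated. Tumor and plasma data are intact, so it would be wrong to conclude that the primary endpoint as a whole fails or that the study's main question goes unanswered.

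The count assumes one tube per time, as in 6.11, and staff who work from the numbered steps. The absence of a whole-blood procedure is asserted for the protocol text available. The laboratory details to which the shipment instructions point were not visible, and a separate laboratory manual was not seen. The volume conclusion rests on the assumed hematocrit and recovery ranges. It shows that a shared tube is usually adequate, not that it always is.

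**What to change.** - **Add a whole-blood step in 11.3.** After mixing and before centrifugation, transfer a whole-blood aliquot to its own labeled tube and freeze it. The bioanalytical laboratory should specify the volume, stabilizer, time limit and storage temperature. The step must fit within the existing 10-minute limit to centrifugation.
- **Or draw a second K2EDTA tube at each time point.** This is safer where plasma volume is tight.
- **Amend 6.11** so that the number and type of tubes agree with 11.3.
- **If no whole-blood assay is planned,** delete blood as a matrix from the Protocol Summary, 2.1, 3.1 and 4.1, and align the storage sentence in 11.3.

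The cost is a wording amendment plus either nine small tubes and slightly less plasma per draw, or nine extra 3 mL tubes for the study (3 x 3 mL = 9 mL more blood per patient). Deleting the matrix costs wording only, but gives up the whole-blood measurement.
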